6.21.2. Subject Withdrawal of Consent

Subjects will be able to withdraw consent for study treatment, or discontinue from all study activities, at any time by their own volition with no impact on any future care they may require at the institution where the study is conducted.

Discontinuing study treatment does not withdraw consent for study follow-up. Subjects who wish to discontinue study treatment should continue to be followed unless they specifically also withdraw consent for continued follow-up.

Note that initial consent to participate in the study also irrevocably grants the Sponsor access to any data or specimens collected from the subject during the study. The subject may withdraw consent to participate at any time, but any data and research specimens collected prior to that withdrawal of consent remain in the study and remain the property of the Sponsor.

6.21.3. Study Withdrawal - Early Termination Procedures

Subjects who discontinue study treatment will have their EOS period planned, and safety follow up until that visit is completed (refer to the SOA in [Appendix 1](#) and [Appendix 2](#)).

6.21.4. Lost to Follow-up

Subjects who do not present for study visits may be considered lost to follow-up only after the site has exercised and documented appropriate due diligence to attempt contacting the subject.

Prior to assessing a subject as lost to follow-up, the site must document at least 3 contact attempts on 3 separate days (using contact information and preferred mechanism as previously indicated by the subject), followed by a certified letter to the subject's last known address.

6.22. Discontinuation of the Study

The study will be discontinued if the Sponsor judges it necessary for any reason, including Sponsor acceptance of a CRC recommendation to stop the study for safety.

6.23. Appropriateness of Measurements

All procedures and assessments used to evaluate the safety and tolerability of study drug are widely used and generally regarded as reliable, accurate, and relevant. The specific safety monitoring, including clinical laboratory assessments, ECGs, and EEGs, are commonly used to assess healthy volunteers participating in a first-in-human study.

7. QUALITY CONTROL AND ASSURANCE

A study startup/investigator training will be held for all sites prior to first subject enrollment. To ensure accurate, complete, and reliable data, the Sponsor or its representatives will do the following:

- Provide instructional material to the study sites, as appropriate.
- Conduct a startup training session to instruct the investigators and study coordinators. This session will give instruction on the protocol, the completion of the eCRF, and study procedures.
- Make periodic visits to the study site.
- Be available for consultation and stay in contact with the study site personnel by appropriate communication media.
- Review and evaluate eCRF data and use standard computer checks to detect probable errors in data collection.
- Conduct a quality review of the database.

In addition, the Sponsor or its representatives will periodically check a sample of subject data recorded against source documents at the study site (refer to [Section 9.6](#)). The study may be audited by the Sponsor or its representatives, and/or regulatory agencies at any time.

Investigators will be given notice before an audit occurs.

To ensure the safety of subjects in the study, and to ensure accurate, complete, and reliable data, the investigator will keep records of laboratory tests, clinical notes, and subject medical records in the subject files as original source documents for the study. If requested, the investigator will provide the Sponsor, applicable regulatory agencies, and applicable ethical review boards with direct access to original source documents (refer to [Section 9.10](#)).

8. PLANNED STATISTICAL METHODS

8.1. General Considerations

Kinoxis, or an appropriately qualified delegate, will be responsible for statistical analysis of all study data for the final clinical study report. The final analysis will be performed after all subjects have completed the EOS visit or discontinued the study. Other than analyses for CRC cohort reviews, no interim analysis is planned for this study.

Data will be summarized descriptively by study medication (placebo and treatment cohort). In addition, select safety and PK summaries may include pooled summaries with all subjects receiving a single dose. The descriptive summaries for the categorical variables will include counts and percentages. The descriptive summaries for the continuous variables will include means, medians, standard deviations, 25th and 75th quartiles, and minimum and maximum values. Unless specified otherwise, all data will be listed for all randomized subjects.

All confidence intervals will be 95%, unless stated otherwise.

Further details of definitions will be provided in a statistical analysis plan.

8.2. Determination of Sample Size

This study is descriptive in nature, and no formal comparisons or hypothesis testing will be performed between study medications or dosing levels. As such, no prospective calculations of statistical power have been made. The sample size has been selected to provide sufficient information to have preliminary characterization of safety, tolerability, PK and PD of the study drug.

8.3. Analysis Populations

The Safety Set (SAF) will include all subjects who received at least one dose of study treatment. Subjects will be analyzed according to the treatment received. The SAF will be used for all safety summaries.

A Per Protocol Set (PP) will include all subjects who received at least one dose of any amount of KNX100 and do not have major protocol violations. Major protocol violations are defined in

Section 9.9. A final determination of inclusion in the PP will be made by a blinded team prior to database lock and unblinding. The PP set may be used on select biomarker endpoints. Analyses conducted with the PP will be based on the assigned study medication.

For the PK assessment, the set of subjects will include those subjects who received at least one of study drug and had sufficient plasma KNX100 concentration data for calculation of PK parameters.

8.4. Demographics and Baseline Characteristics

Summary statistics will be provided for demographic and baseline characteristics in each analysis population and by cohort. No formal statistical comparisons will be performed. Demographic and baseline characteristic data for each subject will be provided in data listings.

8.5. Study Endpoints

8.5.1. Primary Safety Endpoints

The primary safety endpoints include:

- Incidence of TEAEs and TESAEs, related AEs, AEs leading to discontinuation, and AEs by severity.
- Clinical laboratory testing from protocol-specified standard urine and blood tests, including liver function tests (LFTs) and thyroid function tests (TFTs: triiodothyronine [T3], thyroxine [T4], thyroid stimulating hormone [TSH]).
- Change in clinical observations from baseline, including body temperatures, vital signs, ECGs, EEGs.

8.5.2. Secondary Pharmacokinetic Endpoints

The secondary PK endpoints include:

- Maximum observed concentrations (C_{max}) following dose administration.
- Time of C_{max} (T_{max}) following dose administration.
- Area under the concentration-time curve (AUC) from time zero to last quantifiable concentration (AUC_{0-last}), from time zero to 24 hours postdose administration (AUC_{0-24}), and, as data permit, from time zero to extrapolated to infinity ($AUC_{0-\infty}$).
- As data permit, additional disposition parameters including terminal half-life ($t_{1/2}$), volume of distribution (V_z/F), and oral clearance (CL/F) may be calculated.
- Accumulation ratio (RAC) for C_{max} and AUC_{0-24} ; Day 7 vs Day 1 (MAD phase only).
- Other PK parameters will be calculated as deemed appropriate and as referred to in [Section 8.7](#).

8.6. Statistical Analysis of Safety Variables

Safety endpoints for this study are provided in [Section 8.5.1](#).

Summaries of safety data will be performed using the SAF. AE data will be coded to system organ class and preferred term using MedDRA. The MedDRA version will be specified in the study-specific data management plan (DMP).

The number and percentage of subjects experiencing any TEAEs, overall and by system organ class and preferred term, will be tabulated. TEAEs will also be summarized by severity and relationship. Treatment-related events, and other events will be listed. Concomitant medications will be summarized using frequency and percentage of subjects. Results and changes from baseline in vital signs, ECG readings, EEG, and hematology and clinical chemistry parameters will be tabulated at each visit. Abnormal ECG and laboratory findings will also be summarized.

Individual subject listings of prior and concomitant medications, EEG, vital signs, ECG data, and laboratory measurements will be provided.

In addition, ECG parameters will be analyzed as follows (data listings):

- 450 ms <QTcF/ QTcB ≤ 480 ms
- 480 ms <QTcF/ QTcB ≤ 500 ms
- 500 ms <QTcF/ QTcB
- 30 ms <QTcF/ QTcB change from baseline ≤ 60 ms
- 60 ms <QTcF/ QTcB change from baseline

8.7. Statistical Analysis of Pharmacokinetic Variables

PK endpoints for this study are provided in [Section 8.5.2](#). PK concentrations and parameters will be listed and summarized by dose, treatment group, and measurement time using appropriate descriptive statistics. The actual sampling times will be used in the parameter calculations, and PK parameters will be derived using standard non-compartmental methods. Where possible, the following PK parameters of KNX100 and any measurable metabolites will be determined:

- Following the single-dose part of the study:
 - Maximum plasma concentration (C_{max}), time to C_{max} (T_{max}), terminal rate constant (λ_z), terminal half-life ($t_{1/2}$), area under the plasma concentration-time curve from zero to 24 hours (AUC_{0-24}), from zero to the time of the last measurable concentration (AUC_{0-t}) and from zero to infinity ($AUC_{0-\infty}$), apparent plasma clearance (CL/F), apparent volume of distribution (V_z/F), mean residence time (MRT).
- Following the multiple-dose part of the study:

- Maximum plasma concentration (C_{\max}), time to maximum C_{\max} (T_{\max}), minimum plasma concentration (C_{\min}), area under the plasma concentration-time curve from zero to the end of the dosing interval (AUC_{0-24}) will be assessed on both Day 1 and Day 7. The apparent oral plasma clearance (CL/F), the apparent volume of distribution (Vz/F), the terminal $t_{1/2}$, and the AUC extrapolated to infinity will be calculated on Day 7 (and Day 1 if data permit). The extent of accumulation following multiple dosing (accumulation ratio [RAC]) will be evaluated for C_{\max} and AUC_{0-24} .

The C_{\max} and T_{\max} parameters will be determined through the concentration-time profiles. Where possible, the λ_z will be calculated by log-linear regression of the terminal portion of the concentration-time profiles where there are sufficient data and the $t_{1/2}$ will be calculated as $\ln 2/\lambda_z$. The AUC_{0-t} and the AUC_{0-24} will be calculated using the linear trapezoidal rule. Where appropriate, the AUC_{0-t} will be extrapolated to infinity using λ_z to obtain AUC_{INF} . The AUC will be calculated using the linear trapezoidal rule. CL/F will be determined as $\text{dose}/AUC_{\text{INF}}$. Vz/F will be determined as $\text{Dose} / (AUC_{\text{INF}} * \lambda_z)$.

Where possible, the appropriate PK parameters will also be determined for the metabolite (s) of KNX100.

Concentrations below the limit of quantification (BLQ) will be treated as zero for descriptive statistics. Mean BLQ concentrations will be presented as BLQ, and the standard deviation (SD) and coefficient of variation (CV) will be reported as not applicable. Missing concentrations will be excluded from the calculations.

8.8. Interim Analysis

No interim analysis is planned for this study.

9. ADMINISTRATIVE CONSIDERATIONS

9.1. Investigators and Study Administrative Structure

This study is sponsored by Kinosis Therapeutics Pty Ltd. (Kinosis). Information related to participating sites and investigators, qualified physicians, clinical laboratories, members of the CRC, and other relevant administrative personnel will be kept in the Study Master File.

9.2. Human Research Ethics Committee Approval

The study protocol and informed consent, as well as any amendments ([Section 9.14](#)), will be reviewed by the responsible HREC in accordance with Good Clinical Practice (GCP) prior to initiation at a particular site. Any member of the HREC who is directly affiliated with this study as an investigator or as site personnel must abstain from the vote on this study.

The HREC will be asked to document the date of the meeting at which the favorable opinion or approval was given along with a list of the members and voting members present. The favorable opinion or approval must also clearly identify the study along with the study protocol and information statement and informed consent form versions reviewed. Where possible, copies of the meeting minutes should be obtained.

Documentation from the HREC will be filed in the Investigator Site File. A copy will be filed in the Sponsor Study Master File at Kinosis or with a designated organization.

Relevant safety information will be submitted to the HREC during study execution in accordance with national regulations and requirements. In the event of an SAE, the investigator, or Sponsor where applicable, will notify the relevant HREC of any SAEs and safety reports according to local regulation requirements (refer to [Section 6.17.11](#) for more information regarding reporting SAEs).

9.3. Ethical Conduct of the Study

The Sponsor will conduct the study in accordance with the ethical principles that have their origin in the Declaration of Helsinki, are consistent with the GCP guidelines of the ICH, and according to applicable regulatory requirements.

The investigator, head of the medical institution, or designee will promptly submit the protocol to applicable ethical review boards.

As indicated in [Section 9.5](#), an identification code assigned for each subject will be used in lieu of the subject's name to protect the subject's identity when reporting all study-related data.

9.4. Subject Information and Consent

A copy of the HREC approved version of the consent form will be provided to the Sponsor. Subjects who are identified as potentially being suitable to participate in the study will be given an information statement and consent form as approved by the Sponsor and by the site's HREC. The consent form will describe the purpose of the study, the procedures to be followed, and the risks and benefits of participation.

The original signed consent form must be maintained at the site and made available for inspection, as appropriate. Additional information about the subject information and consent process is provided in [Section 6.1](#).

9.5. Subject and Study Confidentiality

Subjects will be identified by their assigned subject number in all written communications between the investigator and Sponsor or its designees. Subject confidentiality is strictly held in trust by the participating investigators, research staff, and the Sponsoring institution and their agents, at a minimum complying with applicable local regulation. This confidentiality is extended to cover testing of biological samples and genetic tests in addition to the clinical information relating to participating subjects.

The study protocol, documentation, data, and all other information generated will be held in strict confidence. No information concerning the study or data will be released to any unauthorized third party, without prior written approval of the Sponsor.

Authorized representatives of the Sponsor, the HREC and regulatory agencies may inspect all documents and records required to be maintained by the site investigator (refer to [Section 9.6](#)). All laboratory specimens, evaluation forms, reports and other records that leave the site will be identified only by the Subject Identification Number (SID) to maintain subject confidentiality.

All study-related information provided by the Sponsor or its designees to the investigator and not previously published (including, but not limited to, the active study agent identity, the IB, the study protocol, verbal and written communication, study data, assay methods and scientific data), will be considered confidential. In addition, all information developed during the conduct of the clinical investigation of the study agent is also considered confidential. Neither the investigator nor any of his/her employees or agents shall disclose or use this information for any purpose other than the performance of the clinical study. Such information shall remain the confidential and proprietary property of the Sponsor, and disclosure to others will be limited to other physicians who are conducting studies with the same active study agent, the HREC, and the applicable regulatory authorities except by prior written permission of the Sponsor or its agents. At such time that information becomes widely and publicly available through no fault of the investigator, the obligation of nondisclosure toward that particular information will cease.

9.6. Case Report Forms and Study Records

Study data will be recorded/filed in subject medical files (source data) and transcribed into an electronic data capture system/CRF for reporting. All required study data will be entered onto the Sponsor-provided eCRF. All information in the eCRFs must be supported by original data in the subject's medical records. All medical records, laboratory printouts, notes made by the physician, and other materials, such as x-rays, will be considered source data and must be available for inspection by the Sponsor, the Sponsor's delegates, or government representatives.

9.6.1. Data Collection

Appropriate training prior to study initiation at that site will be conducted to assist with making entries and corrections to data entered into an eCRF. The site investigator is responsible for maintaining adequate case histories of study subjects, including accurate eCRFs and source documentation (where the source documents are distinct from the CRFs). The site investigator is responsible for the completeness, accuracy, legibility, and timeliness of the data reported; however, the investigator may exercise this responsibility by delegating the actual data collection, recording, and checking activities to appropriately qualified staff under the investigator's supervision.

Information in the database will refer to each study subject by a unique SID. Study subjects will not be identified by name, although the study data will, of necessity, include other personally identifying information such as date of birth.

9.6.2. Source Data

The site investigator is responsible for maintaining adequate and accurate source documents of all observations and data generated during this study. Source documents are the original documents, data, and records from which the subject's eCRF data are obtained. These include, but are not limited to, hospital records, clinical and office charts, laboratory and pharmacy records, radiographs, and correspondence. eCRF entries may be considered source data if the eCRF is the site of the original data recording or as defined in the eCRF completion guidelines or study manuals.

9.7. Study Monitoring

The study will be regularly monitored by a Sponsor representative contract research organization (CRO) according to ICH-GCP standards to ensure quality of the data, preservation of the rights and safety of subjects, and to ensure that the study is being conducted according to the protocol and to ethical and relevant regulatory requirements. The Sponsor or designee will assure the selection of qualified investigators, appropriate program centers, and review protocol procedures with the investigators and associated personnel prior to the program and during periodic monitoring visits.

The Sponsor or a designee will review eCRFs for accuracy and completeness during on-site monitoring visits and after their return from the clinical site. Data entered into eCRFs will be monitored by monitors that are adequately trained on the system. To ensure accurate, complete, and reliable data, the investigator will keep records of laboratory tests, clinical notes, and subject medical records in the subject files as original source documents for the program. The investigators will be required to agree to access by the Sponsor/Sponsor representatives to study documentation, including subject medical files and test results, for monitoring and auditing

purposes, and also to inspections by Regulatory Authorities or quality assurance auditors as requested. Discrepancies will be resolved with the investigator as appropriate.

The Sponsor or its designee will monitor the program using any of the following methods:

- Telephone contacts,
- Site visits, and
- Review of original subject records, CRFs, drug accountability, storage, and general program documentation.

The Sponsor reserves the right to terminate the program if access to source documentation of work performed in this program is denied to the Sponsor or regulatory representatives.

All SAEs will be reviewed within time frames mandated by company procedures and local regulatory requirements. All deaths and SAE reports will be reviewed by the clinical team during study execution to assure completeness and accuracy.

9.8. Cohort Review Committee

An independent CRC will oversee the progress of this study and periodically review the accruing safety data. The CRC is intended to ensure that treatment does not pose undue risk to subjects.

The CRC will include an appropriate group of professional specialties, including at a minimum, the following core individuals:

- Blinded PI or delegate (delegation only when the PI is not available and must be a physician).
- Blinded medical monitor or delegate (must be a physician).
- Blinded neurologist with expertise in EEG analysis and interpretation.
- Blinded pharmacokineticist

The roles, responsibilities, constitution, and operations of the CRC (including its specific composition and schedule for its assessments) will be described in the CRC Plan, which will be reviewed and signed by each member before the first subject is randomized and treated.

9.8.1. Blinded Data Review

For Part A (SAD), the CRC will review all safety and PK data of the Sentinel subjects, collected up to the 30-hour postdose timepoint, to enable decision to enroll the rest of cohort. The CRC will also conduct a blinded, cohort-escalation review after the final subject in a cohort has been dosed, using safety data from all subjects through at least the 30-hour-postdose visit, as well as

all available blinded PK and safety data from the current or previous cohorts. Upon acceptance of reviewed data, dosing for the 2 sentinel subjects in the next cohort may occur.

For Part B (MAD), the CRC will review all safety and PK data from each cohort collected up to and including the 24-hour post morning dose timepoint on Day 8. Additionally, the frequency and severity of the following events and findings will be used to determine the acceptability of escalation to the next cohort:

- Serious AEs
- Discontinuation of participation due to an AE
- Adverse events
- Clinically significant laboratory, EEG and ECG findings.
- Study medication sensitivities and reactions.

The safety observation period may be extended if additional safety data are required for any cohort. Based on all available data, a recommendation for dose escalation or changes to the protocol will be made in collaboration with the investigator.

Updated dispensing guidelines for each dose escalation will be provided based on all available data. Sponsor representatives will document cohort-escalation decisions in central files.

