3. INVESTIGATIONAL PLAN

3.1. Overall Study Design and Plan

This is a Phase 1, FIH, single site, single treatment, 2-part, double blind, placebo controlled, randomized, single ascending dose (SAD)/multiple ascending dose (MAD) study designed to evaluate the safety and tolerability of KNX100 as compared to placebo. This study will enroll healthy volunteers.

The planned enrollment is approximately 64 male and female subjects. The total number of subjects will depend on the number of dose levels assessed in dose-escalation. Completed subjects will have received either KNX100 (active study drug) or placebo. Subjects who discontinue will be replaced to achieve the targeted number of evaluable subjects in each cohort.

Healthy subjects who meet all eligibility criteria will be sequentially enrolled and assigned to a single cohort in Cohorts 1-4 in Part A of the study or in Cohorts 1-3 in Part B of the study. Each cohort selected will evaluate 8 subjects; 6 subjects will be randomly assigned to receive KNX100, and 2 subjects will be randomly assigned to receive placebo. Each cohort will be enrolled sequentially, and the subsequent dose increase will be based on the Cohort Review Committee (CRC) evaluation of data known to date.

Additional cohorts may be added as required, based on safety profile and CRC authorization.

Part A (SAD) will initially dose 2 sentinel subjects (one with KNX100 and one with placebo) in Cohort 1. The center will review safety and tolerability up to and including the 48-hour timepoint for the sentinel subjects before dosing the remaining subjects in the dose cohort. The CRC will be informed and authorize the decision to continue with the remainder of the cohort dosing. Each subject will receive 1 dose, administered orally, of study drug. All subjects in each cohort will have their data, up to and including the 30 -hour postdose timepoint, evaluated for safety and tolerability by the CRC before opening the next dose cohort based on assessment of all available data. The dosing schedule may be extended if additional observations are needed at a particular cohort. In the absence of unacceptable AEs, the CRC may decide to open the next cohort before they have reviewed all data from all 8 evaluable subjects who have completed up to and including the 30-hour timepoint postdose.

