3.2. Rationale for Study Design and Control Group

Study Design: This study is a 2-part, single site, single treatment, double-blind, randomized, placebo-controlled, dose escalating study to assess the safety, tolerability, and PK of single and multiple ascending doses and twice daily dosing of KNX100 administered orally to healthy males and females. Investigators and subjects will be blinded to treatment; however, the site pharmacist will be unblinded. Members of the CRC will be blinded; however, specific members may be unblinded to enable evaluation of PK and safety data for dose escalation decisions if required.

The design of this study is typical of those used for FIH studies with a "dose leader" (sentinel) design to better manage the safety aspects of the study. A sentinel design will be implemented during Part A, (SAD), with 2 subjects being dosed on the first dosing day of each Cohort. Of these, one will receive KNX100, and one will receive placebo. Safety and tolerability will be reviewed for these 2 sentinel subjects by the site, and CRC, before dosing the remaining subjects in the dose cohort.

All data for subjects in each SAD cohort collected up to and including the 30-hour samples postdose will be evaluated for safety and tolerability before opening the next higher dose cohort. In each MAD cohort, data for subjects up to and including the 24-hour timepoint post morning dose on Day 8 will be evaluated for safety and tolerability before opening the next higher dose cohort. The dosing schedule may be extended if additional observations are needed at a particular cohort. In the absence of unacceptable AEs, the CRC may decide to open the next

cohort before having reviewed data from all of the evaluable subjects who have completed Day 7 in the SAD cohorts and Day 14 in the MAD cohorts.

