5.3.4. Dose Escalation

An evaluable subject is one that has been dosed, completed all assessments, and had their data reviewed by the CRC.

Blinded data to be reviewed by the CRC for each subject will include (as a minimum): PK (up to 30 hours postdose for Part A and 24 hours postdose for Part B), EEG, ECG, vital signs, pulse oximetry, neurological examination, and any adverse events.

The CRC may approve dose escalation following review of cohort data if:

- No drug related SAE's occurring within 48 hours of administration of KNX100 or placebo is observed in any subject in the dose group under evaluation.
- No drug related AE's of Grade 3 or greater are observed in 2 or more subjects within a dose group.
- The mean KNX100 C_{max} **OR** AUC does not exceed 84.9 ng/mL or 82.7 ng×h/mL respectively **and** the mean KNX100A C_{max} **OR** AUC does not exceed 26.5 ng/mL and 45.7 hr × ng/mL, respectively, the exposure associated with 1/10th of the NOEL of 2.75 mg/kg observed in the 14-day dog EEG study.
- No emergence or evidence of other PI-deemed and or medical monitor-deemed clinically significant abnormal vital signs, neurological and physical examination, or safety parameters postdose have been observed.

Dose increases will be permitted once review of data from all evaluable subjects has been performed.

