6.20.2. Maximum Tolerated Dose Definition

The maximum tolerated dose (MTD) is defined as the dose below a non-tolerated dose and therefore can only be determined by the observation of a dose level, which is no longer considered acceptable in healthy subjects.

In this study, a dose will be considered non-tolerated and dose escalation will cease if 2 or more subjects in a cohort experience an AE of Grade 3 or higher occurring within 48 hours of administration of KNX100 or placebo at the dose level. Once the non-tolerated dose is defined,

the MTD will be confirmed at the previous dose level below the non-tolerated dose, or a dose between the non-tolerated dose and the last tolerated dose may be investigated. If the dose-escalation scheme is successfully completed for all escalating doses, 35 mg/day will be the highest dose studied (refer to [Section 5.3.2](#) and [Section 5.3.3](#) for the dosing schedule).

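### Part A's 48-hour escalation criteria cannot be confirmed from scheduled data, because 6 of 8 subjects per cohort have no contact between 30 hours and the Day 7 visit; Part B has a similar gap only if the 48 hours runs from each dose

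*Protocol*

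**What the plan says.** **The criteria.** The first bullet of Protocol 5.3.4 permits escalation only if no drug-related SAE "occurring within 48 hours of administration of KNX100 or placebo is observed in any subject in the dose group under evaluation". Protocol 6.20.2 adds that "dose escalation will cease if 2 or more subjects in a cohort experience an AE of Grade 3 or higher occurring within 48 hours" of dosing.

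**The data required, Part A.** Protocol 9.8.1 describes a cohort-escalation review "using safety data from all subjects through at least the 30-hour-postdose visit", after which "dosing for the 2 sentinel subjects in the next cohort may occur". SAP 3.4 sets the same 30-hour minimum. Under Protocol 3.1 subjects are discharged at 30 hours. The 48-hour phone call in Protocol 5.3.1 and Appendix 1 (footnote 2) is for sentinel subjects only. The next scheduled contact for everyone else is the Day 7 (±2) visit.

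**The data required, Part B.** The review in Protocol 9.8.1 uses data "collected up to and including the 24-hour post morning dose timepoint on Day 8". The next contact is Day 14 (±2).

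**Timing of the decision.** Protocol 5.3.4 states "An evaluable subject is one that has been dosed, completed all assessments, and had their data reviewed by the CRC" and allows increases after all evaluable subjects have been reviewed. Protocol 3.1 (Part A, repeated in SAP 3.1) adds that, absent unacceptable AEs, "the CRC may decide to open the next cohort before they have reviewed all data from all 8 evaluable subjects". Protocol 3.2 allows opening "before having reviewed data from all of the evaluable subjects who have completed Day 7 in the SAD cohorts" and, for Part B, before Day 14 data are reviewed.

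**The concern.** An escalation rule needs data that cover its own window. Here the rule looks at 48 hours, while the data requirement stops at 30 hours in Part A and at Day 8 in Part B. For most Part A subjects no one is scheduled to ask about the remaining hours before the follow-up visit. A criterion of no related SAE within 48 hours would then be met by default, because nothing had been volunteered, and not because anyone had checked.

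This matters because the study is first-in-human and Protocol 6.17.5 identifies a potential seizure risk. The protocol already treats 48 hours as the right observation time for sentinels, since their cohort-mates wait for it. Moving to a higher dose carries no equivalent requirement for the six non-sentinels.

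**Working it through.** The plan gives no figure to reproduce; the check is one of timing. Uncovered time = 48 h minus the hours from the dose to the data cut.

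**Part A inputs:** window 48 h (5.3.4, 6.20.2); minimum cut and discharge at 30 h (9.8.1, 3.1, SAP 3.4); 8 subjects per cohort, 6 on KNX100 (5.2); 2 sentinels, one on KNX100, with a 48-h call (5.3.1).

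- Uncovered: 48 − 30 = 18 h; 18/48 = 37.5%.
- Subjects without a 48-h contact: 8 − 2 = 6 of 8; on KNX100, 6 − 1 = 5 of 6.
- Over the three planned escalations (Cohort 1 to 2, 2 to 3, 3 to 4): 6 × 3 = 18 of 24 subjects; 5 × 3 = 15 of 18 on KNX100.
- Earliest next contact: Day 5 is 4 × 24 = 96 h after dosing (Appendix 1, Day 7 ±2), or 5 × 24 = 120 h if counted as 7 ± 2 days after the last dose (6.15).

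A CRC that meets at, say, 60 or 72 h is past the window but still has no scheduled enquiry about hours 30 to 48 for those six. Waiting does not create the data.

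**Part B inputs:** hours counted from the first dose. Cohorts 1 and 2 are dosed at 0, 24, …, 144 h, and Day 8 falls at 168 h (Appendix 2, footnote 2, ±1 h). The text does not say which dose starts the 48 h, so both readings are shown.

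| Reading | Covered at Day 8 | Uncovered |
|---|---|---|
| From first dose only | window ends at 48 h, before 168 h | 0 h |
| From each dose: dose 6 (120 h) | 168 − 120 = 48 h | 0 h |
| From each dose: dose 7 (144 h) | 168 − 144 = 24 h | 24 h (50%); 23 to 25 h with the ±1 h |

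At nominal times doses 1 to 6 are fully covered. Taking all seven windows together, 144 + 48 = 192 h, of which 24 h (12.5%) is uncovered. Two planned escalations depend on this (1 to 2, 2 to 3): 8 × 2 = 16 subjects, 6 × 2 = 12 on KNX100.

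In Cohort 3 the last dose is at 144 + 8 = 152 h, so 168 − 152 = 16 h is covered and 32 h is not. It is the last planned cohort, so this matters only if cohorts are added.

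**The case against.** The strongest objection is that 30 hours is a data cut-off and not a decision time. Protocol 5.3.4 requires PK to 30 h (24 h in Part B) and EEG for each subject, and makes approval depend on mean exposures staying under the caps. Protocol 6.14 has samples frozen and shipped to a bioanalytical laboratory. No turnaround is stated, but if it exceeds 18 h in Part A or 24 h in Part B, the window has closed before any decision. Subjects are also housed from Day -3, which may delay first dosing further. This objection stands. A reader might infer that new sentinels would be dosed while the previous cohort is still inside its 48 hours; the documents do not show that to be likely. It does not answer the main point, because a late decision still lacks a scheduled enquiry about hours 30 to 48.

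Second, the evaluable-subject definition, read strictly, would make the CRC wait for all assessments. The early-opening clauses weaken that reading, though within limits: the clause in 3.1 and SAP 3.1 sits in the Part A text and applies only without unacceptable AEs, and the clause in 3.2 only removes the need to wait for Day 7 or Day 14. None of these clauses authorises ignoring the 48-hour criteria, but none supplies a 48-hour contact either.

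Third, there are other safeguards. Observation may be extended (9.8.1). SAEs must be reported within 24 h once the site knows of them (6.17.11). The Grade 3 bullet in 5.3.4 and the stopping rules in 6.20 have no 48-hour limit, and 6.20.2 still applies to events learned of later. The CRC Plan, which sets the review schedule, was not available. These reduce the consequence. Extension is optional, however, and reporting starts only when the site becomes aware.

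**Conclusion.** The plan is wrong as written on this point. For Part A the finding is firm: in each cohort 6 of 8 subjects, 5 of 6 on KNX100, have 18 of the 48 criterion hours (37.5%) with no scheduled adverse event enquiry before Day 7 (±2), so the CRC cannot confirm the 48-hour criteria from scheduled data whenever it meets before that visit. For Part B the finding is conditional. If the window runs from each dose, the last dose in Cohorts 1 and 2 has 24 of 48 hours covered at Day 8 and the earlier doses are complete; if it runs from the first dose, there is no gap.

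Two further readings are not supported. A reader might infer that the final maximum tolerated dose would be wrong, but AEs are collected to Day 7 in Part A and Day 14 in Part B, so late-discovered events still count. A reader might also infer that a call would detect epileptiform activity. It would not; it finds clinical events only. The correction should be made because it is cheap and lets the protocol's own safety criteria be checked in a first-in-human study.

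**What to change.** 1. Appendix 1 and 5.3.1: extend the 48-hour phone call to all Part A subjects.
2. Protocol 3.1, 3.2 and 9.8.1, and SAP 3.1 and 3.4: require AE and SAE data through 48 hours postdose (in Part B, after the last dose) for all dosed subjects before the next cohort is dosed. State that the early-opening clauses do not override this.
3. Protocol 5.3.4 and 6.20.2: state that in Part B the 48 hours runs from each dose. Appendix 2: add a call 48 hours after the last dose.

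**Cost.** Calls: 6 × 4 = 24 in Part A and 8 × 3 = 24 in Part B, 48 in all, of which 6 × 3 + 8 × 2 = 34 bear on the five planned escalations. Added wait: at most 18 h per Part A escalation and 24 h per planned Part B escalation, so at most 3 × 18 + 2 × 24 = 102 h (4.25 days) in a study planned for about 12 months, and probably none once PK turnaround is counted. If cohorts are added after Part B Cohort 3, the wait there is at most 32 h. The rest is wording in the protocol and SAP.
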